6.2.1. Study Completion and End of Trial

This study will be considered complete (that is, the scientific evaluation will be complete) after all patients have been discontinued from the treatment and have completed protocol defined follow-up period.

“End of trial” refers to the date of the last visit or last scheduled procedure for the last patient.

6.3. Discontinuations

6.3.1. Discontinuation of Patients

The criteria for enrollment must be followed explicitly. If the investigator site identifies a patient who did not meet enrollment criteria and who was inadvertently enrolled, the sponsor must be notified. If the sponsor identifies a patient who did not meet enrollment criteria and who was inadvertently enrolled, the investigator site will be notified. A discussion must occur between the sponsor clinical research physician (CRP) and the investigator to determine whether the patient may continue in the study, with or without investigational product. Inadvertently enrolled patients may be maintained in the study and on investigational product when the Lilly CRP agrees with the investigator that it is medically appropriate for that patient. The patient may not continue in the study with or without investigational product if the Lilly CRP does not agree with the investigator’s determination that it is medically appropriate for the patient to continue. The investigator must obtain documented approval from the Lilly CRP to allow the inadvertently enrolled patient to continue in the study with or without investigational product.

In addition, patients will be discontinued from the study drug and from the study in the following circumstances:

- Enrollment in any other clinical trial involving an investigational product or enrollment in any other type of medical research judged not to be scientifically or medically compatible with this study.
- Investigator/Physician Decision
 - the investigator/physician decides that the patient should be discontinued from the study.
 - if the patient, for any reason, requires treatment with another therapeutic agent that has been demonstrated to be effective for treatment of the study indication, discontinuation from the study occurs prior to introduction of the other agent
- Patient Decision
 - the patient requests to be discontinued from the study
- Sponsor Decision
 - Lilly stops the study or stops the patient’s participation in the study for medical, safety, regulatory, or other reasons consistent with applicable laws, regulations, and good clinical practice (GCP)
- The patient has evidence of progressive disease.
- The patient experiences unacceptable toxicity.
- The patient is noncompliant with study procedures and/or treatment (Section 7.6).

- The patient's treatment is delayed for more than 14 days as the result of a drug-related AE (refer to Section 7.2.4) upon discussion with Lilly CRP.

Patients who discontinue will have follow-up procedures performed as shown in the Study Schedule ([Attachment 1](#)).

6.3.2. Discontinuation of Study Sites

Study site participation may be discontinued if Lilly, the investigator, or the ethical review board (ERB) of the study site judges it necessary for any scientific, medical, safety, regulatory, ethical, or other reasons consistent with applicable laws, regulations, and GCP.

6.3.3. Discontinuation of the Study

The study will be discontinued if Lilly, while considering the rights, safety, and well-being of the patient(s), judges it necessary for any scientific, medical, safety, regulatory, ethical, or other reasons consistent with applicable laws, regulations, and GCP.

7. Treatment

7.1. Materials and Supplies

LY3009120 will be supplied up to a maximum dose strength of 100 mg capsules for oral consumption. LY3009120 capsules should be stored within the temperature range stated on the label. Investigators should instruct patients to store the capsules at home in the original container and to keep out of the reach of children. Capsules should not be opened, crushed, or dissolved.

Clinical study materials will be labeled according to the country's regulatory requirements.

7.2. Study Drug Administration

The investigator or designee is responsible for:

- explaining the correct use of the investigational agent(s) and planned duration of each individual's treatment to the patient and, if appropriate, to the patient's designated legal representative,
- verifying that instructions are followed properly,
- maintaining accurate records of study drug dispensation, and collection, and
- returning or destroying all unused medication to Lilly or its designee at the end of the study.

Patients will be instructed to contact the investigator as soon as possible if they have a complaint or problem with the study drug(s) so that the situation can be assessed.

7.2.1. Dosing Schedule

During both the dose-escalation phase (Part A) and the dose-confirmation phase (Part B) LY3009120 will be administered orally BID daily in a 28-day cycle. **In Part A only:** on Cycle 1 Day 1, the evening dose should be omitted to enable characterization of a full PK profile. The protocol may be amended to explore alternative schedules as a result of interim PK/PD data collection and analysis. During all cycles, study drug should be taken at approximately the same time. Oral study drug will be taken at least 2 hours after and 2 hours before any food intake.

Patients should take study drug at least 2 hours after their last meal/snack and wait at least 2 hours before eating again. Water consumption will be allowed at any time, while the same guidelines provided for food intake should be followed for any other liquid consumption. Any deviations should be documented in the patient diary. If a patient misses or vomits a dose, that dose should be omitted.

During Cycle 1 and Cycle 2, patients will record the time of dosing and number of capsules taken in a diary. Clinic personnel will instruct patients to pay particularly close attention to record this information accurately on days of PK assessments ([Attachment 4](#)).

For Cycle 2 and beyond, a delay of ≤ 7 days in the start of a cycle (Dose 1) for justifiable reasons (for example, inclement weather, holidays, or weekends) other than toxicity will be permitted and does not constitute a protocol violation. To allow for recovery from toxicity, a delay of

≤14 days in the start of a cycle (Dose 1) will be permitted for Cycle 2 and beyond and does not constitute a protocol violation.

7.2.2. Dose Escalation Phase

By nature of being a dose-escalation study, data will be evaluated on an ongoing basis until the maximum tolerated dose (MTD) is determined.

Safety data, in particular adverse events (AEs), will be the primary criteria for the dose escalation. In addition, if available at the time of dose escalation decision, pharmacokinetics (eg, C_{max} , AUC, and CL) results will be used as secondary/supporting data for dose escalation. No dose escalation can occur without prior discussion and agreement between the investigator and the Lilly study team; the decision will be documented in writing.

Based on the ongoing safety reviews, modifications to the dose escalation strategy or other design elements may be made via protocol amendment to ensure patient safety.

7.2.2.1. Dose-Limiting Toxicity Determination and Maximum Tolerated Dose Definition

Dose-limiting toxicity (DLT) is defined as an adverse event (AE) during Cycle 1 for a patient enrolled in Part A that is possibly related to the study drug and fulfills any one of the following criterion using the National Cancer Institute's (NCI) Common Terminology Criteria for Adverse Events (CTCAE) v4.0:

- ≥CTCAE Grade 3 non-hematological toxicity. Exceptions will be made for:
 - Nausea, vomiting, diarrhea, or constipation that can be controlled with appropriate care. Grade 3 and Grade 4 nausea, vomiting, or diarrhea should be considered DLT if persisting more than 48 hours despite maximum supportive intervention.
 - Grade 3 elevations of ALT and/or AST lasting fewer than 8 days, without evidence of other hepatic injury, in the setting of preexisting hepatic metastasis and baseline elevation of these values, may not be considered a DLT if agreed by the study investigator and Lilly CRP.
 - Grade 3 rash that resolves or improves to a Grade 2 or less within 7 days and remains tolerable may not be considered a DLT if agreed by the study investigator and Lilly CRP/CRS.
- CTCAE Grade 4 hematological toxicity of >5 days duration.
- Grade 4 thrombocytopenia of any duration
- Grade 3 thrombocytopenia with bleeding
- Grade 3 febrile neutropenia
- Any other significant toxicity deemed by the primary investigator and Lilly clinical research personnel to be dose limiting (for example, any toxicity that is possibly related to the study medication that requires the withdrawal of the patient from the study during Cycle 1).

Investigators, together with the Lilly CRP, can declare a DLT if a patient is experiencing increasing toxicity during treatment, and it becomes clear that it is not going to be possible to complete the treatment without exposing the patient to excessive risk.

A DLT-equivalent toxicity is defined as an AE occurring between Day 1 and Day 28 of any cycle (other than Cycle 1) for a patient enrolled in Part A or in any cycle for a patient enrolled in Part B (including Cycle 1) that would have met the criteria for DLT if it had occurred during Cycle 1 for a patient enrolled in Part A.

For the purpose of this study, the MTD is defined as a safe dose that has the highest probability of DLT in the targeted toxicity interval (20 to 35%). A safe dose means that the probability of DLT larger than 35% is below 25%.

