7.2.3. Dose Confirmation Phase

Once the MTD has been defined, the dose-confirmation phase will be opened. Enrollment will be expanded by approximately 45 additional evaluable patients with advanced unresectable/metastatic melanoma and NSCLC. The dose(s) to be studied in Part B will be defined at the end of dose escalation after a safety, PK, and PD review. These dose(s) will not exceed the MTD.

If DLT-equivalent toxicities in the first cycle (that is, toxicities that would meet the DLT criteria in Section 7.2.2.1) occur in 33% or more of patients within this confirmation phase, then investigators and the Lilly CRP will assess the nature and severity of these toxicities. No additional patients will be accrued until this safety review is completed and a decision is made either to continue at the current dose or to de-escalate the dose and define a new dose for the confirmation portion. If DLT-equivalent toxicity occurs in one third or more of patients during

Cycles 1 or 2 of Part B (with a minimum of 6 patients enrolled), the enrollment of new patients will cease until the Lilly CRP or CRS and study investigators assess the severity and nature of the toxicity.

The safety review and decision will be documented in writing.

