1.5 Simulation Studies

We perform simulations under different scenarios to investigate the operational characteristics: Toxicity band method vs. traditional 3+3.

- 3-patient cohorts starting from the lowest dose. No dose skipping.
- Maximum number of patients: 33
- Stopping rules for Tox-band method: max sample size reached or the recommended next dose has been treated for 9 Patients:

We considered 8 scenarios to represent a wide range of possible curves. The true DLT rate of the MTD is fixed at 25% across scenarios. Scenario 1 and 2 are toxic cases that have MTD at the first and second level. Both scenario 3 and 4 (in blue color) have 300 mg at the MTD with either steep or flat curves. Similarly, we design scenario 5 and 6 to have the same MTD at 400 mg. Scenario 7 has MTD at 500 mg, whereas scenario 8 is a safe case that the MTD is at the last dose.

[figure not shown]

Figure 3. The Pre-specified probability of DLT under each scenario

Table 2. The Pre-specified probability of DLT under each scenario

	Pre-specified Prob. of DLT							
Dose	1	2	3	4	5	6	7	8
50	0.25	0.14	0.07	0.02	0.03	0.01	0.05	0.01
100	0.4	0.25	0.09	0.04	0.05	0.03	0.07	0.02
200	0.55	0.40	0.13	0.09	0.09	0.05	0.11	0.05
300	0.65	0.55	0.25	0.25	0.14	0.09	0.14	0.08
400	0.75	0.65	0.36	0.47	0.25	0.25	0.17	0.11
500	0.85	0.75	0.48	0.65	0.36	0.5	0.25	0.15
600	0.90	0.85	0.60	0.80	0.47	0.65	0.40	0.18
700	0.95	0.90	0.75	0.90	0.60	0.80	0.55	0.25

We ran 1000 simulations under each scenario to investigate the operating characteristics of the Toxicity Band and 3+3 methods. The results are summarized in Table 3 and 4.

Table 3. Probability of each dose selected as MTD, mean number of subjects, and mean percentages of a DLT under each scenario: Results based on 1000 simulations (Toxicity Band Method)

Dose	Scenarios							
	1	2	3	4	5	6	7	8
50	0.833	0.422	0.084	0.008	0.015	0.002	0.031	0
100	0.159	0.464	0.159	0.068	0.072	0.019	0.138	0.018
200	0.008	0.109	0.247	0.333	0.105	0.047	0.121	0.038
300	0	0.005	0.342	0.512	0.274	0.313	0.126	0.093
400	0	0	0.136	0.076	0.337	0.527	0.204	0.120
500	0	0	0.028	0.003	0.152	0.086	0.233	0.138
600	0	0	0.003	0	0.027	0.005	0.095	0.137
700	0	0	0.001	0	0.018	0.001	0.052	0.456
Mean # of Subj.	10.035	14.358	21.585	22.479	25.020	25.710	25.266	28.977
Mean % of a DLT	39.20	27.54	19.57	17.62	16.26	15.73	15.93	10.79

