5.1. Endpoint Definitions

5.1.1. Safety Endpoints

All patients who receive at least 1 dose of LY3009120 will be evaluated for safety and toxicity. Safety measures that will be used in the study include adverse event (AE), dose limiting toxicity (DLT), clinical laboratory test results, vital signs and electrocardiograms (ECG). In addition, after each cohort, the toxicity-band method will be used to summarize the posterior distribution of probability of a DLT. All AEs will be classified and graded using the National Cancer Institute Common Terminology Criteria for Adverse Events (NCI CTCAE) version 4.0.

Dose Limiting Toxicity:

Dose-limiting toxicity (DLT) is defined as an adverse event (AE) during Cycle 1 for a patient enrolled in Part A (Dose Escalation) that is possibly related to the study drug and fulfills any one of the following criterion using the National Cancer Institute's (NCI) Common Terminology Criteria for Adverse Events (CTCAE) v4.0:

- \geq CTCAE Grade 3 non-hematological toxicity. Exceptions will be made for:
 - Nausea, vomiting, diarrhea, or constipation that can be controlled with appropriate care. Grade 3 and Grade 4 nausea, vomiting, or diarrhea should be considered DLT if persisting more than 48 hours despite maximum supportive intervention.
 - Grade 3 elevations of ALT and/or AST lasting fewer than 8 days, without evidence of other hepatic injury, in the setting of preexisting hepatic metastasis and baseline elevation of these values, may not be considered a DLT if agreed by the study investigator and Lilly CRP.
- CTCAE Grade 4 hematological toxicity of >5 days duration.
- Grade 4 thrombocytopenia of any duration
- Grade 3 thrombocytopenia with bleeding
- Grade 3 febrile neutropenia
- Any other significant toxicity deemed by the primary investigator and Lilly clinical research personnel to be dose limiting (for example, any toxicity that is possibly related to the study medication that requires the withdrawal of the patient from the study during Cycle 1).

Investigators, together with the Lilly CRP, can declare a DLT if a patient is experiencing increasing toxicity during treatment, and it becomes clear that it is not going to be possible to complete the treatment without exposing the patient to excessive risk.

DLT-Equivalent Toxicity:

A DLT-equivalent toxicity is defined as an AE occurring between Day 1 and Day 28 of any cycle (other than Cycle 1) for a patient enrolled in Part A or in any cycle for a patient enrolled in

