5.8. Safety Analyses

All patients who receive at least 1 dose of LY3009120 will be evaluated for safety and toxicity. Adverse event terms and severity grades will be assigned by the investigator using CTCAE, Version 4.0).

Safety analyses will include summaries of the following:

- adverse events, including severity and possible relationship to study drug
- dose adjustments
- laboratory values
- vital signs
- DLTs at each dose level
- ECG readings

In addition, after each cohort, the toxicity-band method will be used to summarize the posterior distribution of probability of a DLT.

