5.8.2. Dose Limiting Toxicity

Dose limiting toxicities (DLT) will be listed for all patients on therapy in Part A. DLT-equivalent toxicities will also be listed for all patients on therapy in Parts A and B. A Toxicity Band method (described in Protocol Appendix 10) will be used to assist the decisions related to dose escalation and determination of the MTD.

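### The SAP's DLT definition omits the protocol's exception for transient, tolerable Grade 3 rash, so two definitions govern the outcome behind the MTD

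*Protocol*

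**What the plan says.** Protocol 7.2.2.1 makes any possibly related Grade 3 or higher non-hematological toxicity in Cycle 1 of Part A a DLT, with three exceptions:

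1. gastrointestinal events that can be controlled with appropriate care;
2. short-lived Grade 3 ALT/AST elevation in patients with liver metastases and raised baseline values, if agreed;
3. rash: "Grade 3 rash that resolves or improves to a Grade 2 or less within 7 days and remains tolerable may not be considered a DLT", again only "if agreed by the study investigator and Lilly CRP/CRS".

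SAP 5.1.1 sets out the same definition with the same opening criterion, the same first two exceptions and the same later bullets. Its last exception is the one for "Grade 3 elevations of ALT and/or AST lasting fewer than 8 days, without evidence of other hepatic injury". The next bullet is the Grade 4 hematological criterion.

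The SAP then uses the term. SAP 5.8 asks for DLTs at each dose level and states that "the toxicity-band method will be used to summarize the posterior distribution of probability of a DLT". SAP 5.8.2 asks for listings of DLTs and DLT-equivalents and says that the toxicity-band method "will be used to assist the decisions related to dose escalation and determination of the MTD".

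**The concern.** The SAP presents a complete definition of its own. Under that text, a possibly related Grade 3 rash in Cycle 1 of Part A remains a DLT even after the investigator and sponsor have agreed, as the protocol allows, that it is not one. The SAP defines a DLT-equivalent as an event that would have met the DLT criteria, so the gap carries into later Part A cycles and Part B.

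DLT is the only outcome the dose-toxicity model uses. The model identifies the MTD, the MTD caps the Part B dose, and the primary objective is a recommended Phase 2 dose. If the two texts stand, the reported DLT listing, the DLT summary by dose and the reported posterior can each include a patient who was not a DLT when the dose was chosen.

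**Working it through.** **Comparing the texts**

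| Exception to the Grade 3 or higher non-hematological criterion | Protocol 7.2.2.1 | SAP 5.1.1 |
|---|---|---|
| Controlled GI events | yes | yes |
| Transient Grade 3 ALT/AST elevation, if agreed | yes | yes |
| Transient, tolerable Grade 3 rash, if agreed | yes | absent |

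Three readings that might close the gap were checked.

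- *A cross-reference.* SAP 5.3.2 and 5.8.2 send the reader to Protocol Attachment 10 for the toxicity-band design. That attachment uses the term DLT but does not define it. Nothing in the SAP cites 7.2.2.1, and the word rash does not appear in the SAP.
- *The SAP's discretionary bullet.* The clause on other significant toxicities can only add DLTs. It cannot remove one.
- *Redaction or superseded text.* Both passages are current and unredacted at this point, and the summary of Amendment (d) does not touch the rash exception.

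The Part B pause rule is not affected, because Protocol 7.2.3 ties it to "toxicities that would meet the DLT criteria in Section 7.2.2.1".

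**What one reclassified patient does to the model**

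The documents state no figure for this, so it was computed from the design in Attachment 10. Inputs:

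- Model (1.2, 1.3): logit p(d) = α + β log(d/700).
- Prior (1.4): (α, log β) bivariate normal, mean (−0.092, 0.359), SD (2.507, 0.907), ρ = 0.282.
- Rule (1.2): drop doses with P(p > 0.35) > 0.25; of the rest, take the one with the highest P(0.20 < p ≤ 0.35).
- Cap: at most one level up, following the simulation set-up (1.5), "3-patient cohorts starting from the lowest dose. No dose skipping".
- Assumed data: 0/3 at every lower dose.

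As a check, the prior medians in Attachment 10 Table 1 were reproduced first. The slope is [logit(0.5) − logit(0.005)] / log(700/50) = 5.293/2.639 = 2.006. This returns 0.005, 0.020, 0.075, 0.155, 0.246, 0.337, 0.423 and 0.500, as printed.

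The posterior was then computed on a numerical grid. Recommended next dose (mg BID) with 3 patients at the current dose:

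| Current dose | 0/3 | 1/3 | 2/3 |
|---|---|---|---|
| 50 | 100 | none | none |
| 100 | 200 | 100 | 50 |
| 200 | 300 | 200 | 100 |
| 300 | 400 | 300 | 200 |
| 400 | 500 | 400 | 300 |
| 500 | 600 | 500 | 400 |
| 600 | 700 | 600 | 500 |
| 700 | 700 | 700 | 600 |

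Two examples:

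- At 300 mg, moving from 0/3 to 1/3 raises P(p > 0.35) at 400 mg from 0.055 to 0.327. That exceeds the limit of 0.25, so escalation becomes a stay.
- At 50 mg, the same move raises the overdose probability at 50 mg from 0.012 to 0.259, and no dose is admissible.

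Number of doses (of 8) at which one added DLT changes the recommendation:

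| Patients at current dose | 0 vs 1 | 1 vs 2 | 2 vs 3 |
|---|---|---|---|
| 3 | 7 | 7 | 6 |
| 6 | 0 | 7 | 7 |
| 9 | 0 | 6 | 2 |

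The total is 42 of 72.

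The conduct text (Protocol 6.2 and 7.2.2.2) limits the increment to 100% and does not itself forbid skipping a level. Under that cap the 0 vs 1 counts rise to 4 of 8 with 6 patients (at 200, 300, 400 and 500 mg) and 3 of 8 with 9 patients (at 200, 300 and 400 mg). The other counts are unchanged.

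**The case against.** The strongest reply is that the model figures show how a small-cohort design reacts to any extra DLT and say nothing specific about rash. For the MTD to move, an exempted event would have to enter the model as a DLT. Dose decisions are taken by the investigators and the sponsor's physician under the protocol, and they would know which rash had been exempted. Attachment 10 is part of the protocol, so its use of DLT most naturally means the 7.2.2.1 definition. No separate refit on the SAP definition is described. The exemption is also discretionary and narrow: without agreement, the two texts give the same result.

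Much of this stands. It makes the reporting outputs the surest place for a discrepancy: the DLT and DLT-equivalent listings and the DLT summary by dose. The dose-recommendation figures should be read as the sensitivity to one reclassified patient, not as a forecast.

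It does not reconcile the two definitions. SAP 5.8 and 5.8.2 place the posterior and the MTD determination in the same document as the narrower list of exceptions, and an analyst following that document would count the exempted rash. The figures also depend on the escalation cap, but replacing the one-level cap with the 100% increment limit makes one reclassified DLT matter more, not less.

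**Conclusion.** The concern holds. SAP 5.1.1 is wrong as written: it restates the protocol's DLT definition without one of its three exceptions and does not defer to the protocol.

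The texts diverge only for a possibly related Grade 3 rash that improves to Grade 2 or less within 7 days, remains tolerable and is exempted by agreement. Where that happens, one patient's DLT status differs between the documents, and in a cohort of three that is often enough to change the model's recommendation. The model figures assume the stated prior, no DLTs at lower doses and one-level escalation.

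The frequency cannot be estimated because the documents give no rash rate. The SAP version leads to more DLTs and lower doses, not to overdosing. The point should be fixed, but it does not call the design into question.

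**What to change.** Either add the Grade 3 rash exception to SAP 5.1.1, including the requirement for agreement between the investigator and the sponsor's physician or scientist, or replace the repeated list with a statement that Protocol 7.2.2.1 is the sole DLT definition. The cross-reference is the safer choice because it prevents further drift between the documents.

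State that this one definition applies to the toxicity-band fits, the DLT listing, the DLT summary by dose level and the DLT-equivalent listings. Then check that every Grade 3 rash already adjudicated has been classified under it.

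The cost is one bullet or one sentence in the SAP plus that check. Design, sample size and data collection do not change.
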